### **Telehealth Study**

Outpatient individuals experiencing suicidality will learn of the study opportunity from their outpatient provider. Interested outpatients will complete the enrollment process with a researcher over computer screenshare and/or telephone. This includes eligibility screening, informed consent, and randomization to JAH or CAU. The baseline and follow-up assessments will be scheduled at the end of the call. Participants will be paid \$25 for each completed assessment.

The baseline assessment will be conducted remotely via Zoom, a HIPAA-compliant video conference site. A brief semi-structured telephone interview and online survey measures will be administered to collect data including the participant's experience with suicidality, depressive and anxiety symptoms, stress, coping with acute distress, satisfaction with outpatient care and JAH. Participants assigned to the JAH condition will be oriented to the Jaspr Health app through Zoom screenshare, and will complete (via telehealth) a comprehensive suicide assessment within Jaspr. Based on the Suicide Status Interview (SSI) from the CAMS approach, the JAH chatbot will also conduct lethal means counseling and assist the participant in building a stability plan as part of the comprehensive assessment. Participants will also be able to select behavioral skills from Jaspr Health to include in their stabilization plan as well as videos of people with lived experience to provide insight, wisdom, and hope. To mimic a telehealth workflow, the researcher will provide access to Jaspr Health via Zoom and guide the participant's engagement with different components of the platform until they have completed the SSI and fully built out their stability plan. Once completed, the Jaspr Health platform will provide the participant with access to JAH. Before concluding the call, the researcher (functioning as a mental health technician) will ensure the participant is able to download, register, and reliably use JAH on their PC, phone, tablet, or other hardware.

We will schedule three brief (5-10 minutes) support check in calls with each participant to take place at 72 hours, one week, and three weeks after they receive access to their study materials (JAH or safety planning packet). During these calls, a researcher will answer any questions about the app or the safety planning materials, inquire if they are using the materials, and assess any barriers to use. These calls are similar to getting a call from a medical provider's office (not from the provider themselves, but office staff) to check in on their patient after surgery or other procedure to check in on pain, comfort, got what they need; our staff will be checking in on the participants. Just as the office staff member making the call doesn't delve into the specifics of the medical problem, we also won't delve into their suicidality or other problem behaviors. If the participant needs, warm handoff procedures will be used to connect them with a crisis counselor at Boys Town.

The follow-up assessments conducted at 30- and 90-days after the baseline assessment will include the online survey measures and a semi-structured interview. The researcher will send a reminder the day before each appointment using the method of contact preferred by the participant (i.e., email or text). At the time of the scheduled follow-up appointment, the researcher will call the participant's primary phone and subsequently attempt to reach them via text and email if there is no answer. During the follow-up assessments, the researcher will send the participant a link to complete the online surveys and verbally provide their study ID number. After the surveys are completed, the researcher will proceed to the semi-structured interview which will include questions collecting information such as the participant's thoughts and experience with suicide since the prior study session and their use of resources (JAH and the crisis stability plan, if applicable). The debrief interview from the UWRAMP will be conducted following each assessment. In the event that the participant meets or exceeds the distress threshold, we will utilize the Warm Handoff procedure and connect the participant to a crisis counselor at Boys Town, as described above.

All participants will be given access to use JAH for 30-days should they wish to do so following the completion of their final study assessment.

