The ED study will also include provider participants who will be asked to complete a demographics survey and a brief interview about each of their index study patients after their intervention with the patient is complete. The brief interview will be administered in-person and assess the provider's feeling of preparedness for the assessment, the patient's degree of distress at the time of encounter, helpfulness of Jaspr's clinical support tool in discharge disposition determination, and risk assessment (if applicable).

ED study primary outcome variables include: suicidality (death by suicide, suicide attempts, suicidal ideation), ED/hospital admissions, discharge disposition, use of restraints while in ED (chemical, physical), intensity ratings of acute distress, self-efficacy in coping with distress, use of imminent distress intervention and coping skills, and helpfulness of their ED encounter. Jaspr condition-specific outcomes will be examined and reported descriptively. These include tools accessed during and after the ED visit, perceived usefulness and satisfaction of Jaspr brief intervention components, and usage of provider/patient apps and their features.

Telehealth study primary outcome variables include: suicidality (death by suicide, suicide attempts, suicidal ideation); Crisis-related healthcare utilization (ED visits, psychiatric hospitalization, calls to crisis line; crisis calls to therapist; Outpatient Satisfaction; Use of evidence-based interventions to reduce suicide risk (safety planning, lethal means management, behavioral skills). Secondary outcomes include: Reasons for living; Psychological distress (depression, anxiety, stress); Cognitions associated with suicide risk (hope, optimism, pessimism).

The primary hypotheses include:

1. Jaspr patients will report significantly greater decrease in suicidality and ED/hospital admissions than CAU patients from the initial session to follow-up assessments.
2. Jaspr patients will report significantly greater increases in self-efficacy in coping with acute distress, use of acute crisis tolerance skills, and perceived helpfulness of the care they receive compared to CAU patients.
3. Jaspr patients will report high levels of satisfaction with Jaspr.

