#### ED Study

**Patient Participants:** Because the patient's medical treatment is of foremost importance and to accommodate the fluid, unpredictable environments in the ED and to work within their usual flow, the researchers will pause all research procedures whenever necessary to allow for the patient's medical care and resume should there be additional periods of waiting. Once enrollment is complete (i.e., consent is obtained), the researchers will request a release of information from the participant for information we would like to gather from a member of their care team after the patient's discharge. Specifically, we are interested in collecting data about the patient's length of stay, if physical or chemical restraints were used and if so for how long, their final discharge disposition (e.g., if the patient was admitted to inpatient, residential, or substance abuse treatment or discharged to home), and if the patient was admitted whether it was involuntary or voluntary. This data will be obtained orally by speaking with a member of the patient's care team; medical records will not be accessed by the researchers. Permission (or not) for this release of information will not impact the patient's participation in the study (i.e., if they decline to provide permission for this release, they may still participate in the study). If the patient agrees to provide permission for the researcher to collect this information, they will be asked to sign a release of information form.

The researcher will then conduct the baseline assessment and the researcher will randomize the patient to condition while the participant is completing baseline measures. The researcher will inform the patient of the condition they have

been assigned after they have completed the baseline assessment.

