After the post-treatment interview and surveys are completed in the ED, the onsite researcher will explain the purpose of blinding researchers to participants' condition and then virtually introduce (e.g., via Zoom, FaceTime) the patient participant to the (blinded) EBPI research assistant who will be responsible for conducting the post-discharge follow-up assessments. This research assistant will remain blind to the patient's condition during this discussion and the 7-, 30-, and most of the 90-day follow up assessment time points. At the very end of the 90-day assessment, the research assistant will be asking condition-specific questions (e.g., usability questions about the patient's experience with the Jaspr app) and thus cannot be blind during this assessment time point. In an effort to ensure a warm hand-off from the ED-based researcher to the follow-up blinded assessor, the blinded research assistant will schedule the three follow up assessments and administer the Participant Information Form.

Because the site contact or their designee will determine sufficiently stable participants to refer to the research, we do not anticipate that participation in the study will lead to significant distress. However, the researchers will be attentive to changes in mood states and, if indicated, will check in verbally with the participant about whether they wish to continue. If a participant becomes more distressed during the meeting for whatever reason (e.g., due to length of waiting in the ED, an upsetting conversation with medical personnel, or some aspect of the research procedure), the researchers will again ask if they prefer to discontinue the study. We prefer not to automatically discontinue the study in cases where their distress is caused by an aspect of their ED experience for the reason that participation in the study may actually be helpful to them in distracting them from the actual cause of their upset. We will however inquire about their preference to discontinue. We will also inform the site contact or their designee and a member of the patient's care team that the patient appears more upset than at the start of the research procedure. In cases where the patient appears more distressed than they were at the start of the procedure and displays difficulty redirecting to research tasks, we will discontinue the study procedure and notify the site contact or their designee and a member of the patient's care team.

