***Analysis Strategy.*** We will use SPSS Version 23. For patient data, we will use Hierarchical Linear Modeling (HLM). HLM provides greater flexibility in that it can analyze a variety of commonly encountered outcome distributions (e.g., continuous, binary count), test the fit of different covariance matrix assumptions; and include participants who are missing data at some time points. We will account for nesting of patients under providers by including providers as a random effect; we will account for nesting within sites by including dummy coded fixed effects predictors representing site in all analyses. For each outcome, we will specify the correct distribution and compare fit indices to identify the covariance matrix best fitting the data. Many hypotheses relate to change over time, and so the multiple time-points will be treated as nested within the individual. Also, we will treat the intervention conditions (Jaspr and JAH) and time as categorical, dummy-coded predictors; the control conditions and baseline scores will serve as the reference category. The parameter of interest will be the Time X Condition interaction, and the Type III statistic will serve as an omnibus test of whether the two conditions differed in change over time. Regression coefficients will indicate at which follow up time points the conditions showed differential change from baseline. For patient satisfaction as well as the secondary hypotheses concerning medical providers ratings of helpfulness, we will compute descriptive statistics and consider ratings to be favorable using the *a priori* established criteria that 80% or more respondents rate program components as favorable or highly favorable. For the remaining secondary hypotheses, which are based on provider data about patients from both conditions at one time point, we will compute between-condition means. Since it is possible that not all providers will be able to provide data given time constraints inherent in their job, we may not have the statistical power to conduct probability tests. Hence, we will examine the data descriptively to provide preliminary information about efficacy and compute effect sizes to inform future research.

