## **B. Informed Consent**

Patients and providers who are interested in participating will complete a screen for eligibility. As part of the screening process, the potential participants will also answer demographic questions to assess whether our recruitment efforts are reaching a diverse group and to assess the characteristics of participants in the research. Eligible participants will then proceed to the Informed Consent procedure with a researcher, though participants may choose to review the consent form on their own if they prefer. All participants will be provided with an overview of the study and disclosure regarding what will be asked of them using Informed Consent procedures. The Informed Consent form will describe the study procedures and clarify that the study is completely voluntary and that participants may decline to participate at any time. For the ED study, the information provided to patients about Jaspr will be limited until after randomization to guard against disappointment or other negative feeling if assigned to the CAU condition. Once randomized, patients assigned to the Jaspr condition will be provided with the supplemental consent form with complete disclosure of the study procedures and information about Jaspr. These patient participants will have the chance to ask questions about Jaspr and the Jaspr study condition and decide if they want to continue their participation in the study. Once initial eligibility is determined, potential participants will be given a brief description of the study and asked for their verbal consent to proceed with the Informed Consent discussion. The Informed Consent process will take place in person with a member of the research team. The Informed Consent process will take place remotely via telephone and/or internet with a member of the research team.

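### Telehealth patients are randomised before a separately scheduled baseline, and nothing says the arm is withheld until the baseline measures are complete

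*Combined protocol and SAP*

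**What the plan says.** All references are to the combined protocol and SAP.

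- **Section 5.A, Telehealth Study (enrolment).** Interested outpatients enrol with a researcher by telephone or shared screen. The content of that step is given as follows: "This includes eligibility screening, informed consent, and randomization to JAH or CAU. The baseline and follow-up assessments will be scheduled at the end" (when the enrolment call closes).
- **Section 5.A, Telehealth Study (baseline).** "The baseline assessment will be conducted remotely via Zoom", with an interview and online surveys. The paragraph lists these measures first and then describes the orientation of JAH patients to the app. It does not give the interval between the two sessions or say when the patient learns the arm.
- **Section 5.A, ED Study.** The researcher randomises while the patient is filling in the baseline measures and tells the patient which condition they have "been assigned after they have completed the baseline assessment".
- **Section 5.B, Analysis Strategy.** One model serves both trials. Condition and time are dummy-coded, and "the control conditions and baseline scores will serve as the reference category". The Time x Condition interaction is the parameter of interest.
- **Section 3.** Telehealth outcomes include rating scales, such as suicidal ideation, satisfaction and the secondary measures that begin "Reasons for living; Psychological distress (depression, anxiety, stress". They also include events and service use: deaths, attempts, ED visits, hospitalisations and crisis calls.

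**The concern.** A baseline should be measured before allocation can affect it. Here it is measured after randomisation, largely by self-report, and no rule keeps the arm from the patient in between. A patient who knows they have been assigned to usual care, or to the app, may rate ideation, distress or satisfaction differently at baseline for that reason alone.

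Because baseline is the reference level, such a shift enters the change contrast to the extent that it has faded by days 30 and 90. The direction cannot be predicted. Worse baseline ratings among disappointed usual-care patients would give them more room to improve and would favour usual care. Better baseline ratings among JAH patients would leave them less room to improve. The concern is confined to rating scales; it does not extend to the events and service-use outcomes.

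The second issue does not depend on disclosure. A patient lost between the two calls has been randomised but has no baseline outcome. With 30 per arm, a few such losses matter to an intent-to-treat analysis.

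**Working it through.** **1. Order of steps, side by side**

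| Step | ED study | Telehealth study |
|---|---|---|
| Randomisation | while baseline measures are being completed | during enrolment |
| Baseline measures | same session | separate Zoom session, scheduled at the end of the enrolment call |
| Patient told the arm | after baseline | not stated |
| App introduced | after baseline | described after the measures in the baseline paragraph |

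The gap is therefore a stated order of steps plus an absent disclosure rule. Exposure to the app before the baseline measures is not shown. The timing of the usual-care safety-planning packet is not stated.

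**2. Illustration of what a shift could do**

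The plan gives no figure to reproduce. From the documents: 30 per arm, three time points, two-sided 5% level. Assumed: a Gaussian scale, compound symmetry with within-person correlation rho, a shift of s SD in one arm caused by knowing the allocation, fractions p30 and p90 of it remaining at days 30 and 90, no app effect, and no site or provider effects.

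- Arm-difference vector, current order: d = s x (1, p30, p90).
- Arm-difference vector, baseline before disclosure: d = s x (0, p30, p90), because patients still know their arm at follow-up.
- Noncentrality of the Time x Condition F test (df 2, 116): (30/2) x sum of (d - mean d)^2 / (1 - rho).

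Worked case, s = 0.2, rho = 0.5, shift gone by follow-up: d = (0.2, 0, 0), the sum of squares about the mean is (2/3) x 0.04 = 0.0267, and the noncentrality is 15 x 0.0267 / 0.5 = 0.80. The rejection rate is 11.3%.

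All rows below use s = 0.2 and rho = 0.5:

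| Shift remaining at days 30, 90 | Noncentrality, current / changed order | False-positive rate, current order | Changed order |
|---|---|---|---|
| none, none | 0.80 / 0 | 11.3% | 5.0% |
| half, none | 0.60 / 0.20 | 9.7% | 6.5% |
| half, half | 0.20 / 0.20 | 6.5% | 6.5% |
| three quarters at both | 0.05 / 0.45 | 5.4% | 8.5% |
| all, all | 0 / 0.80 | 5.0% | 11.3% |

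With equal persistence p at both follow-ups, the two columns are mirror images about p = 0.5. On this measure the changed order helps below that point, makes no difference at it, and does worse above it.

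**3. Bias in one change coefficient, current order**

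Bias = s x (1 - p). Standard error = sqrt((2/30) x 2 x (1 - 0.5)) = 0.258 SD. With s = 0.2, the bias is 0.2/0.258 = 0.77 standard errors if the shift is gone and 0.1/0.258 = 0.39 if half remains.

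**4. Loss between the calls**

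The documents give no rate. If 5% to 10% were lost (assumed), 3 to 6 of 60 would be randomised with no baseline outcome.

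**The case against.** The strongest objection is that the point rests on silence. Randomisation is listed as an enrolment step, but the text does not say the patient, or the researcher taking baseline, then learns the result. The two sessions could even fall on the same day. This stands: what is shown is an unguarded opening, not disclosure before baseline.

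Second, the changed order does not lower the error rate in every case. The table bears this out, and persistence is plausible: "All participants will be given access to use JAH for 30-days", but only after the final assessment, so usual-care patients go without the app throughout follow-up. The error rates therefore cannot be presented as the gain. The reply is that effects of knowing the arm at days 30 and 90 belong to an open-label comparison under either order, whereas a baseline altered by allocation is no longer a baseline.

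Third, the analysis keeps patients who miss some time points, and the plan intends to collect data from everyone. That helps a patient who misses baseline but returns. It does nothing for one who gives no outcome data at all.

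A reader might also draw three stronger inferences that the documents do not support:

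- *That the plan itself recognises this bias.* Section 7.B keeps ED patients' information about the app "limited until after randomization to guard against disappointment or other negative feeling if assigned to the CAU condition". That concerns patients' feelings. It does not mention baseline measurement, and it runs until randomisation, not until baseline is complete.
- *That the ED study's masked assessor is a missing Telehealth safeguard for baseline.* "This research assistant will remain blind to the patient's condition during this discussion" and for most of the follow-up, but that person enters only after the ED baseline and post-treatment measures.
- *That the ED study masks whoever takes the baseline.* It does not. The researcher who conducts the ED baseline also randomises during it, and only the patient is kept unaware.

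**Conclusion.** The point holds as a low-cost design improvement for the Telehealth study only. Randomisation precedes a separately scheduled baseline, no passage withholds the arm until that baseline is complete, and baseline is the reference for the parameter of interest. Self-reported rating scales are therefore open to an allocation effect of unknown size and direction, and patients can be randomised and lost without a baseline outcome.

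It would go too far to say that Telehealth patients are told their arm before baseline, or that the trial's results will be biased. The shift, its persistence, the correlation and the loss rate are all assumed. The illustration shows only that, with 30 per arm, a modest shift that fades would not be negligible, and that one which fully persists would cancel from the change contrast. The case rests on the soundness of a pre-allocation baseline and on avoiding randomised patients without one. Severity is low to moderate.

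**What to change.** **Preferred.** In section 5.A, Telehealth Study, move randomisation to the existing Zoom call: after the baseline surveys and interview are complete, and before app orientation or the safety-planning packet. This protects the baseline and means that no one is randomised without one.

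**If that is not practical.** Keep the order, but state that the patient is not told the arm until the baseline measures are complete, as the ED study does. Report losses between randomisation and baseline by arm, since withholding the arm does not prevent them.

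**Cost.** A protocol amendment and a small change in call workflow, with no added visits, patients or measures. The alternative costs a sentence and one line of reporting.

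**Limit.** Either change protects the baseline only. Patients will still know their arm at days 30 and 90, and effects of that knowledge on follow-up ratings remain.
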